14.1.2.2 Sensitivity Analyses of SRI-4 and SRI-6

The following sensitivity analyses are planned to be performed using different approaches to the missing data handling from the primary analysis.

Sensitivity Analysis #1: Per Protocol Analysis

The primary analysis method including the missing data handling approach for the two-primary endpoints will be repeated on the PP Analysis Set if the size of this analysis set differs substantially (>10%) from mITT.

For this analysis, the estimated OR, together with associated two-sided 95% CI of the estimated OR and nominal p-value from the logistic regression model, comparing each evobrutinib treatment group to placebo will be presented.

In addition, the number and percentage of SRI-4/SRI-6 responders and non-responders at Week 52 in each treatment group will be presented the same way as for the primary analysis (see Section 14.1.2.1).

Sensitivity Analysis #2: MI

In this analysis, a subject will be considered as a non-responder if using EAC-determined protocol prohibited medications (i.e., EAC-treatment failure). For subjects with missing response at Week 52, then the MI will be used to impute the missing data using the available observations from previous visits and from components of SRI-4/SRI-6 response and also stratification factor used in primary analysis.

The MI analysis will include the components as described below:

1. SLEDAI-2K change from baseline total score will be imputed using SAS MI procedure (including 2 other components: PGA score and BILAG response) and then the occurrence of a ≥ 4 -point reduction will be re-derived from the imputed values. For the SRI-6 the occurrence of a ≥ 6 -point reduction will be also re-derived from the imputed values.
2. PGA score will be imputed using SAS MI procedure (including 2 other components: SLEDAI-2K change from baseline and BILAG response), assuming the distribution is approximately normal. The imputed values will be transformed to a 0-3 scale:
 - i. Negative values will be imputed as 0,
 - ii. Values > 3 will be imputed as 3.
 - iii. The imputed score will then be used to calculate whether there was significant worsening in the PGA score.

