3. Whether there was no new BILAG A organ domain scores and ≤ 1 new BILAG B organ domain score compared to Day 1 will be considered as a dichotomic response with value 1 when it is met and 0 otherwise. This score will be imputed using SAS MI procedure (including 2 other components: SLEDAI-2K change from baseline and PGA score) and the response will be deducted from the logic below:
 - i. Values < 0.5 will be imputed as 0,
 - ii. Values > 0.5 will be imputed as 1.

Components no. 1 to 3 will be imputed assuming a MAR pattern. The SAS MI procedure will be performed as follows:

- Monotone missing data structure will be created as follows: intermediate (non-monotone) missing data will be multiply imputed using the Markov chain Monte Carlo (MCMC) method and assuming MAR and multivariate normality. The SAS procedure PROC MI with the MCMC option will be used with seed number = 2005270018. The number of burn-in iterations will be set to 200, which is the default value. Nevertheless, if diagnosis plots show that the convergence has not yet occurred, this will be adjusted.
- Then, each component will be imputed with treatment group, race, region, SLEDAI-2K total score (<10 ; ≥ 10) and data at previous visit from all SRI components as covariates.

- Imputation will be repeated 1000 times. The SRI response will then be calculated for each of the multiply imputed data sets from the imputed components. For this analysis, the estimated OR, together with associated two-sided 95% CI of the estimated OR and nominal p-value from the logistic regression model, comparing each evobrutinib treatment group to placebo will be presented. Results will be combined using MIANALYZE SAS procedure with the Rubin's rules as described in Appendix 18.9.

The SAS code to implement the MI and MIANALYZE procedures is in Appendix 18.9.

The same analysis method as the primary analysis of the two-primary endpoints will be performed using the mITT Analysis Set for SRI-4 and in the HDA subject subgroup for SRI-6.

In addition, the number and percentage of SRI-4/SRI-6 responders and non-responders at Week 52 in each treatment group will be presented the same way as for the primary analysis (see Section 14.1.2.10) using Rubin's rules to gather binomial proportion by each treatment (see Appendix 18.9).

Sensitivity Analysis #3: Tipping Point Analysis

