14.3.4 HRQoL

The following HRQoL endpoints are summarized in Table 24.

All endpoints are described in Appendices 18.3, 18.4, 18.5, 18.6 and 18.7. They will be analyzed on QoL Analysis Set.

Table 24 : HRQoL analysis

Questionnaire	Score to be analyzed	Analysis Set	Analysis
SF-36 v2	Change in PCS, MCS scores, and their components	
 QoL Analysis Set 	
 Mixed model with repeated measures (MMRM) model Descriptive statistics Distribution %CFB curve Logistic regression
LupusQoL	Change in each domain score	
 QoL Analysis Set 	
 MMRM model Descriptive statistics Distribution %CFB curve
FACIT-Fatigue	Change in Total score	
 QoL Analysis Set 	
 MMRM model Descriptive statistics Distribution %CFB curve Logistic regression
EQ-5D-5L	Change in VAS score, EQ-5D-5L index	
 QoL Analysis Set 	
 MMRM model Descriptive statistics
PGIC	% of subjects with improvement, no change and worsening	
 QoL Analysis Set 	
 Logistic regression Descriptive statistics

MMRM model:

Missing data will be considered as MAR.

The QoL endpoints will be analyzed using the MMRM model, with treatment group, visit, and treatment by visit interaction as the main effects, baseline assessment and randomization strata as covariates. The unstructured covariance matrix will be considered. Denominator degree of freedom will be computed using Kenward and Roger’s method (Kenward 1997).

The LSMEAN estimate of mean change from baseline score, difference of the LS Mean from placebo, 2-sided 95% CI of the difference, and nominal 2-sided p-value of the difference from the model contrast will be presented.

An example of SAS code is available in Appendix 18.9.

Descriptive statistics:

For each treatment group, descriptive statistics will be presented for absolute value, CFB and percent CFB value for each visit, from baseline to Week 52.

In addition, the following will be provided:

- Mean score CFB will be presented as a by-visit line plot for each treatment group, with all treatment groups included in a single figure, and horizontal axis extending to Week 52

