  lsmeans TreatmentGroup* SLEDAI_2K_screening / slicediff= SLEDAI_2K_screening
  oddsratio ilink cl;
  ods output Glimmix.LSMeans.SliceDiffs;
run;
```

Adjusted P-value:

The 12 raw p-values generated (for the two-primary endpoints and two key secondary endpoints with 3 treatment comparisons with placebo) are adjusted based on the hierarchical procedure by applying the methodology described in Section 14.1.2.4 (and further explained in Appendix 18.15). SAS PROC IML presented in Maurer 2014 will be used to generate the final adjusted p-values (i.e. adjusted for multiplicity).

MI process – MAR pattern: PROC MI with SAS

The following SAS code can be used to implement the MI with MAR pattern. The order of the SRI components must follow the one defined in the Section 14.1.2.4.

```
/******
STEP 1 : creation of monotone missing data structure
******/

/** _burn-in_NBITER_ will have to be adjusted by a convergence plot,
if convergence is not yet diagnosed after 200 iterations ***/
title "Step 1 : Create monotone structure" ;
proc MI data=<Dataset> out=outMAR1 seed=&seed. nimpute=&nimpute. noprint;
  var
  TreatmentGroup
  black (0=non-black 1=black)
  SLEDAI_2K_screening
  US (0=not US 1=US region)
  West (0=not Western Europe, 1=Western Europe region)
  Jap (0=not Japan region, 1=Japan region)
  SRIComp1_base SRIComp3_base
  SRIComp1_Day14 SRIComp2_Day14 SRIComp3_Day14

  /* continue to the last endpoint */

  ;
  mcmc chain=single initial=EM nbITER=200 NITER=100 impute=monotone ;
  EM MAXITER = 5000 ;
run ;

/******
```

```
STEP 2 : Apply multiple imputation
*****/
title "Step 2 : Apply MI procedure (MAR pattern)" ;
proc mi data=outMAR1 nimpute=1 seed=&seed. out=outMAR2 noprint;
  by _Imputation_;
  class TreatmentGroup race region SLEDAI_2K_screening;
  var
    TreatmentGroup race region SLEDAI_2K_screening
    SRIComp1change_Day14 SRIComp2_Day14 SRIComp3_Day14

  /* continue to the last endpoint */

;
  monotone regression;
run;
```

Then after applying the needed derivation of SRI score and the logistic analysis of interest for SRI-4, the next step consists in:

```
*****
STEP 4a : Pooling ODDS RATIOS and CI using Log Transformation
*****/
*** Log-transform odds ratio estimates and obtain standard error from confidence
intervals ***;
DATA lgsodds_t;
  SET lgsodds (WHERE=(INDEX(EFFECT,"TRT")));
  log_or_lr_value=LOG(ODDSRATIOEST);
  qn=quantile('NORMAL',.975);
  log_or_lr_se=(LOG(UPPERCL)-LOG(LOWERCL))/(2*qn);
RUN;
*** Combine transformed estimates;

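### The imputation step that carries drop-outs to Week 52 in Sensitivity Analysis #2 omits the continuous Day 1 SLEDAI-2K total and Day 1 PGA, and does not match Step 1 of its own code

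*SAP*

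**What the plan says.** Section 14.1.2.2 describes Sensitivity Analysis #2 in general terms first: "MI will be used to impute the missing data using the available observations from previous visits and from components of SRI-4/SRI-6 response", plus the stratification factors. It then takes the components in turn.

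- **SLEDAI-2K (component 1):** "SLEDAI-2K change from baseline total score will be imputed using SAS MI procedure", and the 4-point or 6-point fall is derived from the imputed change.
- **PGA (component 2):** the score itself is imputed and confined to 0–3. "The imputed score will then be used to calculate whether there was significant worsening in the PGA score". Under 14.1.1, worsening means a rise of 0.3 or more from baseline.
- **BILAG (component 3):** a yes/no indicator of no relevant new A or B grades compared with Day 1.

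The covariates for the final imputation are listed in one sentence: "each component will be imputed with treatment group, race, region, SLEDAI-2K total score" (as <10 or ≥10) and "data at previous visit from all SRI components as covariates".

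Appendix 18.9.1 gives the code in two steps. Step 1 (MCMC, `impute=monotone`) fills intermediate gaps, and its variable list includes "SRIComp1_base SRIComp3_base". Step 2 (monotone regression) imputes everything after drop-out. Its list holds treatment, race, region and the screening SLEDAI-2K class variable, then starts the components at "SRIComp1change_Day14 SRIComp2_Day14 SRIComp3_Day14". No baseline component appears in it. For the order of the components the code refers to Section 14.1.2.4, which is the multiple-testing section and defines no such order.

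**The concern.** Change from baseline usually depends on the baseline value: subjects who start high have more room to fall. An imputation model for change that leaves baseline out gives low-baseline and high-baseline drop-outs in the same stratum, with the same recent history, the same expected change. For PGA the absolute score is imputed without reference to the value against which it will then be compared.

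The missing-at-random assumption is credible only given the variables that predict the outcome. If the baseline mix of drop-outs differs between arms, the errors need not cancel and the odds ratio shifts. This is the only analysis of the two primary endpoints under missing at random. Section 7 drops the completer analysis, and the per-protocol, unadjusted and background-therapy analyses all keep non-responder imputation. The same section enlarges the analysis cohort because of possibly higher drop-out than planned. The SAP's own repeated-measures model for change scores (14.3.4) uses "baseline assessment and randomization strata as covariates"; that is an analogy, not a contradiction, but it shows the usual practice.

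**Working it through.** The SAP states no figure on this point, so there is none to reproduce.

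**1. Which step imputes Week 52 for drop-outs.** Step 1 only makes the missing pattern monotone. A subject who leaves after visit k has nothing intermediate to fill, so visits k+1 to Week 52 come from Step 2. The baseline terms of Step 1 therefore do not reach these values.

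**2. Text against code.**

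| | 14.1.2.2 covariate list | Step 1 code | Step 2 code |
|---|---|---|---|
| Screening SLEDAI-2K | <10/≥10 | included | class variable |
| Day 1 SLEDAI-2K total | no | `SRIComp1_base` | no |
| Day 1 PGA | no | unclear | no |
| History | previous visit | all visits listed | all variables earlier in the list |

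The entry for PGA is unclear for this reason. By the numbering in 14.1.2.2, component 3 is BILAG and Step 1 lacks baseline PGA. But no new grades compared with Day 1 has no natural baseline value, so `SRIComp3_base` may have been meant as PGA.

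**3. Direction of the error.** Let β be the slope of change on baseline B, given the model's other covariates X. Leaving B out gives

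imputed mean change − true mean change = −β × (B − E[B | X]).

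With β < 0, a subject below the average B gets too large a fall and one above it too small a fall. In the contrast these errors cancel if drop-outs deviate from E[B | X] equally in both arms, and otherwise do not.

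**4. Size by baseline level.** Assumed, not from the SAP: 200,000 subjects per scenario; baseline mean 10, SD 3.5; visit-to-visit coefficient 0.6 or 0.85; drop-out after visit 1, 3 or 6; slope of change on baseline −0.5.

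| SLEDAI-2K criterion | Baseline | True | Imputed without baseline |
|---|---|---|---|
| 6-point fall | 10–12 | 38–39% | 44–48% |
| 6-point fall | ≥13 | 60–61% | 48–53% |
| 4-point fall | <7 | 27–28% | 35–39% |

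With slope −0.3 the errors were about 4 to 10 points in the same directions. Adding baseline brought the rates to within about 1.6 points of the truth.

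**5. Size in the treatment difference.** Assumed, not from the SAP: 4,000 per arm, 20 replicates, 13 visits, slope −0.5 for SLEDAI-2K, carry-over 0.5 for PGA. Differences are in percentage points. The range in each cell covers the previous visit only and all earlier visits.

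| Scenario | Endpoint | Full data | Without baseline | Shortfall |
|---|---|---|---|---|
| Similar baseline, about 24% missing | SRI-4 | 14.8 | 14.3 | 0.5 |
| Opposite selection, about 7% | SRI-4 | 14.7 | 14.2–14.4 | 0.3–0.5 |
| | SRI-6 | 13.7 | 12.5–13.1 | 0.6–1.2 |
| Opposite selection, about 24% | SRI-4 | 14.9 | 13.2–13.9 | 1.0–1.7 |
| | SRI-6 | 13.2 | 10.2–12.0 | 1.2–3.0 |
| Stronger selection, about 31% | SRI-4 | 14.7 | 12.1–13.1 | 1.6–2.6 |
| | SRI-6 | 13.6 | 9.0–11.3 | 2.3–4.6 |

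In the 24% case with opposite selection the odds ratios were 1.74–1.79 against 1.86 (SRI-4) and 1.62–1.74 against 1.84 (SRI-6). With both Day 1 values added they were 1.83–1.85 and 1.80–1.82. A variant at 24% with a weaker subject effect gave shortfalls of 1.7–2.4 (SRI-4) and 2.4–3.9 (SRI-6). Across all scenarios the residual after adding both values was about 0.1 to 0.7 point.

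**6. Against sampling error.** With the rates and numbers in 8.2.1, SE = √[(p₀(1−p₀) + p₁(1−p₁))/n].

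- SRI-4: √[(0.40×0.60 + 0.60×0.40)/103] = 6.8 points; 1.7/6.8 = 0.25 SE.
- SRI-6 in HDA (half of 103): √[(0.30×0.70 + 0.55×0.45)/51.5] = 9.4 points; 3.0/9.4 = 0.32 SE.

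**The case against.** The case for leaving this alone has several parts.

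- **Baseline is not wholly absent.** A reader might infer that the model ignores baseline. It does not: the screening stratum is in both steps and Step 1 has two baseline terms. This stands, but those terms do not serve drop-outs.
- **HDA subjects.** A reader might infer that SRI-6 is imputed with no regard to baseline activity because everyone in that subgroup is ≥10. The documents do not support this. SRI-6 is derived from the same imputed change as SRI-4, in a model containing the stratum, so HDA subjects are imputed at their own level. Only variation within HDA is lost.
- **Earlier visits carry part of baseline.** This is true above all for PGA. Among drop-outs in the lowest third of baseline PGA (24% missing, opposite selection), SRI-4 response was 33.9% in full data, 27.8% using the previous visit only and 33.5% using all earlier visits. The sentence in 14.1.2.2 says previous visit, while the Step 2 list as written uses all earlier ones. For SLEDAI-2K, longer history changed the error by at most about 2 points.
- **The code is a sample.** It is abbreviated, but the covariate sentence in 14.1.2.2 has the same gap.
- **Selection in opposite directions by arm was assumed.** Nothing in the SAP indicates it. This stands and limits what can be said about bias.
- **Little depends on it.** The p-values are nominal, the analysis lies outside the testing hierarchy, and the tipping-point analysis does not use this model. This also stands.

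**Conclusion.** The gap is real and confined to Sensitivity Analysis #2. The regression that imputes Week 52 for drop-outs conditions on neither the continuous Day 1 SLEDAI-2K total nor Day 1 PGA, and the two code steps disagree. Within a stratum, imputed response is drawn toward the average over baseline levels.

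A reader might infer that the treatment effect from this analysis is therefore biased, or that the primary result is in doubt. Neither follows. With similar baseline among drop-outs in both arms the contrast is almost unbiased. With opposite selection by arm it was off by about 1 to 3 points at about 24% missing, up to 3.9 in one variant, and by 0.3 to 1.2 points at about 7%. These sizes rest on assumed baseline distributions, slopes and drop-out patterns. In these runs the shift was toward no effect because active-arm drop-outs had the higher baseline; the opposite pattern could reverse it. The primary analysis counts missing responses as non-response and does not use this model.

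Nor can it be said for certain that Step 1 omits baseline PGA, because the meaning of SRIComp3 is not settled. The correction is worth making because it costs almost nothing.

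**What to change.** 1. In 14.1.2.2, name the Day 1 SLEDAI-2K total (continuous) and the Day 1 PGA score as covariates for every component, and say whether the history is the previous visit only or all earlier visits.
2. In 18.9.1, put both Day 1 values ahead of the first post-baseline visit in the VAR lists of Steps 1 and 2, so that every regression conditions on them.
3. Define SRIComp1, SRIComp2 and SRIComp3, and replace the pointer to 14.1.2.4 with one to the list in 14.1.2.2.

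Bounding the imputed SLEDAI-2K change at minus the baseline total is optional. It alters SRI-4 status only for a baseline below 4 and SRI-6 status only for a baseline below 6, whereas 8.2.1 describes screening scores of at least 6, and HDA requires at least 10.

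The cost is two variables already collected, a few lines of code and a sentence of text. No other analysis changes.

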14.1.2.3 Supportive Analyses of SRI-4 and SRI-6

The following supportive analysis will be performed for the two-primary endpoints:

Supportive analysis #1: linear trend test

For each of the two-primary endpoints, a test of linear trend in log odds of SRI response with increasing dose, will be based on an appropriate contrast from the logistic model (i.e., (3, 1, -1, -3)). The p-value reported tests the null hypothesis that the log odds of being SRI responder is the same across treatment groups, against the alternative that the log odds increases linearly with increasing treatment group order.

An example of SAS code is available in Appendix 18.9.

Both p-values based on Wald test and Likelihood ratio test will be presented. They will be added in the summary table of logistic regression.

14.1.2.4 Multiple testing

Based on the cumulative clinical and CCI data from Evobrutinib, it is expected that 50mg BID will be at least as effective as 75mg QD, or more effective than 75mg QD.

To maximize the probability of study success while controlling for the overall type 1 error, statistical testing of the hypotheses associated with the two primary endpoints and the two key secondary endpoints will be performed in a hierarchical manner such that the Evobrutinib dose groups will be compared to placebo from the highest dose to the lowest dose as detailed in the following:

1. The two-primary endpoints will be tested first for the highest dose using a Hochberg Procedure at a 1-sided $\alpha=0.025$. If both null hypotheses are rejected, then go to step 2. If none or only one null hypothesis is rejected, then testing stops.
2. The 1st key secondary endpoint of SRI-4 at week 52 in serologically active subjects for the highest dose will be tested at a 1-sided $\alpha=0.025$. If the null hypothesis is rejected, then go to Step 3. Otherwise testing stops.
3. The 2nd key secondary endpoint of time to first severe BILAG A flare for the highest dose will be tested at a 1-sided $\alpha=0.025$. If the null hypothesis is rejected, then go to Step 4. Otherwise testing stops.
4. Repeat steps 1-3 for the medium dose, and the lowest dose sequentially.

Hochberg adjusted p-values will only be needed if the first step of the multiplicity testing is successful.

The corresponding hierarchical testing diagram using the approach described in [Bretz 2009](#) can be found in Appendix 18.15.

14.1.3 Subgroup analysis of Two-primary Endpoints

To assess the consistency of the two-primary endpoints results among subgroups of subjects (See [Table 4](#)), the analysis will be performed on the mITT Analysis Set using the logistic regression model for the odds of a given SRI response with treatment, subgroup of interest, treatment by subgroup of interest interaction as main effects. The estimated OR, together with associated two-sided 95% CI of the estimated OR and nominal p-value from the model contrast will be presented for each treatment group. The same missing data imputation approach will be used as the primary analysis method. No multiple testing adjustments will be performed.

In addition, a forest plot will be presented for each of the two-primary endpoints for the overall treatment effect and for each subgroup of interest including the OR from logistic model and associated 2-sided 95% CI of the OR.

For subgroup D, the analysis performed on the Japan region will be reported as “Partial Japan” for the PA.

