14.1.2.1 Primary Analysis Method of SRI-4 and SRI-6

The null and alternative hypotheses corresponding to the two-primary endpoints are:

$$H_{0a}: \log(\text{OR}_{4_all}) \leq 0 \text{ versus } H_{1a}: \log(\text{OR}_{4_all}) > 0$$

$$H_{0b}: \log(\text{OR}_{6_HDA}) \leq 0 \text{ versus } H_{1b}: \log(\text{OR}_{6_HDA}) > 0$$

where $\log(\text{OR}_{4_all})$ and $\log(\text{OR}_{6_HDA})$ are the log of odds ratio for SRI-4 in all subjects and SRI-6 in the HDA subjects.

The study will be declared positive if the treatment effect is significant in at least one of the primary endpoints. The global hypothesis testing problem is stated as:

$$H_0: H_{0a} \cap H_{0b}$$

$$H_1: H_{1a} \cup H_{1b}.$$

The global null hypothesis is rejected if one or both individual null hypotheses are rejected.

To account for the multiplicity due to the two-primary endpoints and multiple treatment comparisons with placebo for each primary endpoint, the multiple testing procedure as described in Section 14.1.2.4 will be performed.

In the primary analysis of the two-primary endpoints, a subject could be considered as an SRI-4 or SRI-6 Non-Responder if the subject takes EAC-determined protocol-prohibited medications during the treatment period (i.e., EAC-treatment failure). The EAC will make the final determination on whether the subject should be classified as treatment failure. In addition, a subject with a missing response at Week 52 will be considered a non-responder at Week 52.

The primary analysis of the SRI-4 response at Week 52 among all subjects, and SRI-6 response at Week 52 among HDA subjects, will be based on the mITT analysis set, and analyzed using logistic regression model for the odds of a given SRI response adjusted for the stratification variables used in the randomization (race: black vs non-black, screening SLEDAI-2K total score: <10 vs ≥ 10 and region: US and Western Europe vs Japan vs ROW) and with treatment as a factor. The estimated OR, together with associated two-sided 95% CI of the estimated OR, nominal one-sided p-value and adjusted one-sided p-value ($\alpha=0.025$) from the logistic regression model, comparing each evobrutinib treatment group to placebo will be presented.

If there is model convergence problem due to for example zero cells in covariates, appropriate method will be applied to resolve the issue.

An example of SAS code is available in Appendix 18.9.

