For this analysis, a subject will be considered as an SRI-4 or SRI-6 Non-Responder if the subject takes EAC-determined protocol-prohibited medications during the treatment period (i.e. EAC-treatment failure).

Tipping point analysis will be performed as in Yan 2009, Section 2.3.2.

All possible combinations of success/failure may be posited in the 4 treatments groups. Results are obtained by a random single imputation of possible scenarios (responder or non-responder) to each arm. All possible combinations of imputations of response among subjects with missing response in the placebo group and evobrutinib 25 mg QD, 75 mg QD and 50 mg BID groups. For each combination, the imputed data were combined with the data from subjects with non-missing data and primary analysis.

Assumptions of missing data due to a missing response at Week 52 will be varied to see if there are any tipping points:

Let

$n_1 =$ number of responders out of missing data due to various reasons for placebo

$n_2 =$ number of responders out of missing data due to various reasons for evobrutinib 25 mg QD

$n_3 =$ number of responders out of missing data due to various reasons for evobrutinib 75 mg QD

$n_4 =$ number of responders out of missing data due to various reasons for evobrutinib 50 mg BID

The same analysis method as the primary analysis of the two-primary endpoints will be performed using the mITT Analysis Set for each possible combination of n_1 , n_2 , n_3 and n_4 .

The values of n_1 , n_2 , n_3 and n_4 where the study result will be tipped from statistically significant (not statistically significant) to not statistically significant (statistically significant) will be assessed for plausibility based on the corresponding response rate from each treatment. See Section 14.1.2.4 for the multiplicity adjustment procedure.

Sensitivity Analysis #4: Unadjusted Analysis

The analysis of the two-primary endpoints will be performed on the mITT Analysis Set.

In this analysis, the logistic regression model will be used with only treatment as a factor.

For this analysis, the estimated OR, together with associated two-sided 95% CI of the estimated OR and nominal p-value from the logistic regression model, comparing each evobrutinib treatment group to placebo will be presented.

In addition, the number and percentage of SRI-4/SRI-6 responders and non-responders at Week 52 in each treatment group will be presented the same way as for the primary analysis (see Section 14.1.2.1).

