18.9.1 SRI Response

Logistic regression: PROC LOGISTIC with SAS

The logistic regression can be implemented using the following SAS code:

```
proc logistic data=<dataset> descending;
  class TreatmentGroup(ref='Placebo') Region Race SLEDAI_2K_screening;
  model AVALC(event="Y") = TreatmentGroup Region Race
                        SLEDAI_2K_screening / orpvalue clodds=wald;
  ods output CLoddsWald=CLoddsWald;
run;
```

For primary analysis of the 2-primary endpoints and key secondary endpoint *SRI-4 response at Week 52 among serologically active subgroup*, output the 1-sided p-value ($\alpha=0.025$) as below:

- When the OR favors the active treatment (i.e. $OR > 1$), one-sided p-value = two-sided p-value / 2
- When the OR does not favor the active treatment (i.e. $OR \leq 1$), one-sided p-value = 1 – (two-sided p-value / 2)

The interaction can be implemented using the “*” symbol. For example, the following statement takes into consideration the interaction between treatment and region:

```
proc logistic data=<dataset> descending;
  class TreatmentGroup(ref='Placebo') Region Race SLEDAI_2K_screening;
  model AVALC(event="Y") = TreatmentGroup Region Race SLEDAI_2K_screening
                        TreatmentGroup * Region / orpvalue clodds=wald;
  ods output ParameterEstimates=ParameterEstimates CLoddsWald=CLoddsWald;
run;
```

Linear trend in log odds of SRI response for two-primary and key secondary endpoints: PROC LOGISTIC with SAS

In addition to the standard logistic model, the linear trend test can be implemented using the ESTIMATE and CONTRAST statements:

```
proc logistic data=<dataset>;
  class TreatmentGroup Region Race SLEDAI_2K_screening / param=glm;
  model AVALC(event="Y") = TreatmentGroup Region Race
                        SLEDAI_2K_screening;
  ESTIMATE "SRI response rate trend linear in treatment" TreatmentGroup 3 1 -1 -
3;
  CONTRAST "SRI response rate trend linear in treatment" TreatmentGroup 3 1 -1 -3
/ e;
  ods output
  Estimates=Estimates ContrastTest=ContrastTest;
run;
```

Logistic regression subgroup analysis: PROC GLIMMIX with SAS

In addition to the standard logistic model, the subgroup analysis can be implemented using the following code:

```
proc glimmix data=<dataset>;
  class TreatmentGroup (ref='Placebo') SLEDAI_2K_screening;
  model AVALC(event="Y") = TreatmentGroup SLEDAI_2K_screening TreatmentGroup*
  SLEDAI_2K_screening / alpha=0.05 dist=binary;

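### The subgroup logistic and Cox models omit randomisation strata that the main models adjust for, so subgroup estimates may sit slightly nearer 1 than an adjusted overall estimate

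*SAP*

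**What the plan says.** **Main models.** The primary logistic model for SRI-4 and SRI-6 (SAP 14.1.2.1) is "adjusted for the stratification variables used in the randomization": race, screening SLEDAI-2K (<10 or ≥10) and region. The main Cox model for time to first severe flare (14.2.2.2) carries the same three factors.

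**Subgroup models.** Section 14.1.3 specifies a logistic model with treatment, the subgroup factor and "treatment by subgroup of interest interaction as main effects". The PROC GLIMMIX block headed as subgroup analysis in 18.9.1 agrees: its class statement is "class TreatmentGroup (ref='Placebo') SLEDAI_2K_screening", with no other stratum. The flare subgroup model in 14.2.2.3 and its PROC PHREG code in 18.9.2 have the same three terms.

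**Display.** Section 14.1.3 gives judging consistency as the purpose and says "a forest plot will be presented for each of the two-primary endpoints for the overall treatment effect and for each subgroup of interest". It attributes the plotted odds ratio to the logistic model without saying which one.

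**Elsewhere.** Sensitivity Analysis #4 (14.1.2.2) is an overall analysis in which "the logistic regression model will be used with only treatment as a factor". For the key secondary SRI-4 endpoint in serologically active subjects, 14.2.2.3 repeats the strata-adjusted analysis within HDA and non-HDA, so adjustment is kept there.

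**The concern.** A forest plot for consistency invites the reader to set each subgroup row against the overall row. That comparison is clean only if both rows estimate the same quantity. In a logistic model, leaving out a prognostic covariate that is balanced between arms moves the treatment odds ratio towards 1, with no confounding and no interaction. Hazard ratios behave similarly. If the overall row is adjusted and the subgroup rows are not, the subgroup rows can drift towards 1 together because of the model and not because the effect differs.

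The practice is also uneven. HDA and non-HDA odds ratios for SRI-4 come from an unadjusted model in all subjects and from an adjusted one in serologically active subjects, and no reason is given.

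What is at stake is how a supportive display is read.

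**Working it through.** **1. Which strata are lost.** From Table 4 (8.2.3), against the three factors in the main model:

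| Subgroup | Strata kept | Strata lost |
|---|---|---|
| A (SLEDAI-2K) | SLEDAI-2K | race, region |
| C (race) | race | SLEDAI-2K, region |
| D (region) | region | race, SLEDAI-2K |
| B, E, F (serology, ethnicity, immunosuppressant) | none | all three |

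For SRI-6 in HDA the SLEDAI-2K stratum is constant, so only race and region can be lost.

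**2. Planning inputs (8.2.1).** SRI-4 response is 40% on placebo and 60% on active, with 103 evaluable subjects per arm. The implied odds ratio is (0.60/0.40)/(0.40/0.60) = 2.25. These inputs, with SRI-6 at 30% versus 55% in half the subjects, give 80.5% power for at least one endpoint at an assumed correlation of 0.7. The SAP states 80%.

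**3. One omitted two-level stratum.** Assume equal halves, a 40% control rate, a conditional odds ratio of 2.25 and no interaction. The SAP gives no stratum effects, so the stratum odds ratio is varied.

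- s = ln(stratum OR)/2
- Solve a from ½[expit(a+s) + expit(a−s)] = 0.40
- Active rate p₁ = ½[expit(a+ln 2.25+s) + expit(a+ln 2.25−s)]
- Unadjusted OR = [p₁/(1−p₁)]/(0.40/0.60)

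| Stratum OR | p₁ | Unadjusted OR | Ratio to 2.25 |
|---|---|---|---|
| 1.5 | 59.8% | 2.23 | 0.99 |
| 2 | 59.4% | 2.20 | 0.98 |
| 2.7 | 58.9% | 2.15 | 0.95 |
| 5 | 57.2% | 2.00 | 0.89 |

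For stratum OR 5, the control rates are 21.8% and 58.2% (mean 40%) and the active rates 38.5% and 75.8% (mean 57.2%). Each stratum has an odds ratio of 2.25, yet the pooled one is 2.00.

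**4. Against the precision.** The standard error of the log odds ratio is about √(2/(n × 0.24)) for n per arm. It is 0.284 at n = 103 and 0.402 at n = 51.5 (a half-size subgroup). The 95% limits are the estimate times or divided by exp(1.96 × 0.284) = 1.75 and exp(1.96 × 0.402) = 2.20. The shift ln(2.25/2.00) = 0.117 is 0.117/0.402 = 0.29 standard errors in the half-size subgroup. For stratum OR 1.5 it is 0.02.

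**5. All three strata omitted (subgroups B, E, F).** Here the unadjusted rates are held at 40% and 60%, and the adjusted odds ratio is solved for. From the SAP: 50% HDA and 8.3% Japan. Assumed: 15% Black, 35% US and Western Europe, independent strata.

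| Each stratum OR | Adjusted OR | Unadjusted OR | Ratio |
|---|---|---|---|
| 1.5 | 2.29 | 2.25 | 0.98 |
| 2 | 2.38 | 2.25 | 0.95 |
| 3 | 2.56 | 2.25 | 0.88 |
| 4 | 2.74 | 2.25 | 0.82 |

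Other assumed race and region mixes take the last ratio to 0.80. For SRI-6 in HDA (unadjusted OR 2.85) the ratio runs from 0.99 to 0.83 across all mixes. Even 2.74 against 2.25 is 0.70 standard errors of the overall log odds ratio.

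**6. Between levels of one subgroup.** In the same calculation split by SLEDAI-2K, with race and region dropped, the two levels shrink almost alike: ratios of 0.93 and 0.92 at stratum OR 3.

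**7. Hazard ratios.** The SAP gives no flare rate, so the Cox shift is not quantified.

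**The case against.** A reader might infer that the subgroup odds ratios are simply not comparable with the overall one. The SAP does not establish that. Section 14.1.3 does not identify the model behind the overall row, and an unadjusted overall odds ratio is already planned as Sensitivity Analysis #4. If that one is plotted, most of the artefact disappears. The adjusted odds ratio is the natural reading because it is the primary result, but that is an inference.

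A reader might also infer that 18.9.1 contradicts itself, because another block keeps all strata and adds "TreatmentGroup * Region / orpvalue clodds=wald". That block only illustrates how to code an interaction ("the following statement takes into consideration the interaction between treatment and region"). The block labelled for subgroup analysis matches 14.1.3, so text and code agree on a prespecified choice.

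The flare point is narrower too. The forest plot in 14.2.2.3 is described only for subgroup categories, with no overall row, so a mixed display is not shown there.

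Further, simple interaction models are defensible with four arms, a small Japan stratum and SRI-6 in about half the subjects. The p-values are nominal, and this version of the SAP was written after the primary results had been reviewed.

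All of this stands and limits the point. It does not remove it: the main and subgroup models differ without explanation, adjustment is kept for one subgroup analysis in 14.2.2.3, and the reference row is unspecified.

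**Conclusion.** The point holds as a minor one. The subgroup models omit strata that the main models contain, fully for subgroups B, E and F and partly for A, C and D. With one stratum omitted, an odds ratio of 2.25 becomes about 2.23 to 2.00 for stratum odds ratios of 1.5 to 5. With all three omitted, the fall is about 2% to 18% for stratum odds ratios of 1.5 to 4 (20% in the most unfavourable mix tried). These shifts are inside the confidence intervals, and comparison between levels of one subgroup is little affected.

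The result rests on assumed stratum effects and population mixes, strata balanced between arms, and no true interaction. The effect on the SRI forest plot is conditional on its overall row being the adjusted primary odds ratio. No primary or key secondary decision changes.

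**What to change.** - Add the remaining randomisation strata (race, screening SLEDAI-2K, region, leaving out the factor under study or one that is constant) as main effects in the logistic and Cox subgroup models of 14.1.3 and 14.2.2.3, and in the GLIMMIX and PHREG code.
- Extend the convergence fallback of 14.1.2.1 and 14.2.2.2 to these models. As written, it covers only the main analyses.
- Label the overall row of the SRI forest plot as the adjusted primary odds ratio. If the subgroup models stay unadjusted, plot the Sensitivity Analysis #4 odds ratio as the reference and say so.

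The cost is a few covariates in existing code, with no new data. Small strata such as Japan may give sparse cells. Because this version follows review of the primary results, the adjusted subgroup analyses should be identified in the study report as specified after that review.
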